## 4.1 THE PROPOSED TRIAL

### What is the proposed trial design?

Long term follow-up of a multicentred, randomized trial.

## 4.2 What are the planned trial interventions?

All patients have undergone a standard diagnostic arthroscopy using either single-row or double row fixation.

**Single row fixation:**

Single row fixation is defined as follows: fixation by way of bone anchors, located along a single row parallel to the sagittal axis of the rotator cuff footprint. The exact location of the anchors may occur either within that lateral margin of the footprint, or lateral to the footprint, over the edge of the tuberosity. Either simple or mattress sutures were used at the discretion of the surgeon.

**Double row fixation:**

Double row fixation is defined as follows: fixation by way of bone anchors, located along two rows. The lateral row is parallel to the sagittal axis of the rotator cuff footprint. The exact location of the anchors occurred either within that lateral margin of the footprint, or lateral to the footprint, over the edge of the tuberosity. Either simple or mattress sutures were used at the discretion of the surgeon. The medial row is parallel to the sagittal axis of the rotator cuff footprint. The exact location of the fixation occurred close to the bone/cartilage junction along the medial aspect of the footprint. Mattress sutures were used. An acceptable alternative method of fixation for the medial row consists of the Suretak II (Smith and Nephew). This device consists of a sutureless bioabsorbable implant and anchors the rotator cuff to the bone.

**4.4 What are the proposed methods for protecting against sources of bias?**

**Blinding:** Due to the nature of this surgical trial, the surgeon could not be blinded to the intervention. However, a trained independent assessor will carry out the follow-up assessments and will be blinded. This will minimize the potential for biases introduced by the examiner when performing the physical assessment and recording data. The assessor will not have access to the patient chart prior to the examination. The patient will also be blinded to the treatment assignment. To help reduce the potential for observer bias, the physical examination and the administration of study questionnaires are standardized.

**4.5 What are the planned inclusion/exclusion criteria?**

**Patient Population**

The target population is both men and women of any age that were randomized in the original double versus single row RCT.

**Inclusion Criteria**

1. Randomized in the double versus single row original RCT study

**Exclusion Criteria**

1. Excluded from the original study
2. Withdrawn from original Study
3. Unable or unwilling to provide informed written consent

**4.6 What is the proposed duration of treatment period?**

All patients will come in for one clinic visit and will not be followed any further after all of the imaging and clinic data has been collected.

**4.7 What is the proposed frequency and duration of follow-up?**

Patients are assessed in the clinic by the blinded evaluators at 8 years post operatively. It is anticipated that at this clinic visit approximately 20 minutes will be spent with the assessor.

However, as in all doctors' clinics, some waiting can be anticipated and this can be variable depending on clinic loads and nature of cases.

Radiographic analysis will be done with an ultrasound or MRI at 8 years postoperative. Evaluation of the imaging will be performed by an independent investigator who is blinded to the patient's assigned treatment.

**4.8 What are the proposed primary and secondary outcome measures? (see Appendix A)**

**PRIMARY:**

The Western Ontario Rotator Cuff Index (WORC)(29) is a disease specific evaluation that has proven to be an accurate and valid assessment of function after rotator cuff repair. Because it is specific for rotator cuff disease of the shoulder, it is highly sensitive to small but clinically significant changes in patient function.

**SECONDARY:**

1) The American Shoulder and Elbow Surgeon's (ASES) score is a shoulder specific assessment tool developed by the American Shoulder and Elbow Society for use in all types of shoulder problems (Appendix A)(31). It consists of both patient self-assessment and physician assessment. The patient self-evaluation is divided into two sections: pain and activities of daily living (ADL). Pain is recorded on a visual analogue scale and ADL's are recorded on a numeric scale. The overall score is an equal weight of the two sections and produces a score out of 100. The higher the score, the better the outcome. The physician assessment is divided into four segments: range of motion, physical signs, strength and instability. The results of the physician assessment do not provide a score.

Europeans favor the Constant Score(30) (Appendix A). It has been validated, normalized in comparison to disease free patients and places greater emphasis on range of motion and strength. The European shoulder society has adopted the Constant Score for functional assessment of the shoulder. The Constant Score records a variety of shoulder measurements including an objective test of strength using a spring loaded measuring device. The Constant Score reflects an overall clinical functional assessment. This instrument is based on a 100-point scoring system calculated from a self-assessment portion that evaluates pain and ability to perform tasks of daily living, and a clinical assessment which tests active range of shoulder motion and strength. The higher the score the better the outcome.

2) Further secondary outcomes which will be monitored during the post-operative course include: operative times of the two procedures, complications, and the incidence of revision surgery in each procedure.

The MRI or Ultrasound will determine the healing rates of both procedures. It is imperative to determine the relative healing rates as cuff integrity following surgery correlates with function and strength.

**4.9 How will the outcome measures be measured at follow-up?**

**PRIMARY:**

The patient will complete the WORC questionnaire at 8 years post-operatively. The research assistant will be available to answer any questions.

**SECONDARY:**

1) Patients will complete the ASES and Constant Scores at 8 years post-operatively. The research assistant will be available should the patient have any questions regarding the questionnaires. The patient is then examined by the blinded assessor for the physical

assessment portion of the constant score (Appendix A). The surgeon is the last person to examine the patient and is blinded to the results of the outcomes.

#### **4.10 Details of planned analyses**

##### **Primary:**

The primary analysis involves a comparison of the mean WORC scores between the two surgical treatment groups. This analysis is a two sample independent t-test to assess whether there is a statistically significant difference between groups for the mean WORC scores at 8 years post-operatively. The 5% significance level is employed. The underlying assumption for the WORC score data is that there is a normal distribution. If the sample distribution is determined to depart from normal, then a Wilcoxon rank sum test will be performed.

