## Single Versus Double Row Fixation for Arthroscopic Cuff Repair: A 8 Year Long Term Follow-up of a Randomized, Controlled Trial

### 1. Statement of Objectives

In a previous study, ninety patients undergoing arthroscopic rotator cuff repair were randomized to receive either a single-row or a double-row repair. The primary objective was to compare the Western Ontario Rotator Cuff Index (WORC) score at twenty-four months (from June 2007 to June 2009). Secondary objectives included comparison of the Constant and American Shoulder and Elbow Surgeons (ASES) scores and strength between groups. Anatomical outcomes were assessed with magnetic resonance imaging (MRI) or ultrasonography to determine the postoperative healing rates.

The results of the study published in the Journal of Bone and Joint Surgery – JBJS (Volume 94-A. Number 14. July 18, 2012) are in agreement with other randomized clinical trials comparing single-row and double-row fixation. Our hypothesis that double-row fixation yields superior quality of life outcomes compared with single row lateral fixation was not supported.

No significant differences between the single-row and double-row groups were found in the WORC, ASES, or Constant scores or strength at any time point. However, a smaller initial tear size and double-row repair were associated with a greater healing rate.

The original RCT involved a two-year follow-up period. It is our hypothesis that a longer follow-up period would have been of value. At a mean of 8 years postoperatively, we will follow-up the patients involved in the original RCT and measure the same outcomes that were assessed at 2-years.

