##### **Secondary:**

The secondary analysis involves a comparison of the secondary outcome measures between the two surgical treatment groups. The ASES, Constant Score, and imaging healing rates will be analyzed for differences between the two groups at 8 years. The planned secondary analyses are performed using a 5% significance level. No p-value adjustment is required for multiple outcomes, as treatment effectiveness is based only on the primary variable.

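### The 8-year WORC comparison could use the original trial's WORC scores, at little cost, to guard against attendance that differs by arm

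*Combined protocol and SAP*

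**What the plan says.** Section 4.10 (Primary) gives the whole primary analysis of WORC at 8 years: "This analysis is a two sample independent t-test to assess whether there is a statistically significant difference between groups". The only alternative offered is for non-normal data: "If the sample distribution is determined to depart from normal, then a Wilcoxon rank sum test will be performed". Neither test has a covariate or uses an earlier score. Section 4.10 (Secondary) explains why no multiplicity adjustment is made: "treatment effectiveness is based only on the primary variable".

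The score has one source. Section 4.6 says "All patients will come in for one clinic visit", and section 4.9 says "The patient will complete the WORC questionnaire at 8 years post-operatively". Section 4.5 requires written consent to this follow-up and excludes patients who withdrew from the original trial.

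Earlier WORC data were collected. Section 1 says of the original trial, which randomised 90 patients: "The primary objective was to compare the Western Ontario Rotator Cuff Index (WORC) score at twenty-four months". It reports that no significant differences "were found in the WORC, ASES, or Constant scores or strength at any time point", so WORC was compared more than once. The follow-up is to "measure the same outcomes that were assessed at 2-years".

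The text supplied defines no analysis set and no missing-data method, and does not commit to reporting participation by arm.

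**The concern.** Bringing patients back about 8 years after surgery, with fresh consent, makes incomplete participation foreseeable. Neither planned test has any means of allowing for who fails to return, so the comparison is in effect of attenders. The plan never says this in words. It follows because the 8-year questionnaire is the only data source and no imputation or likelihood-based model is planned.

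Randomisation protects a comparison of attenders only if attendance, and the way it depends on outcome, are alike in the two arms. If either differs, the estimated difference is biased. The conclusion on treatment effectiveness rests on this one comparison, and the earlier WORC scores are the natural means of checking and partly correcting for selective return.

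**Working it through.** **No figure to reproduce.** The plan states no sample size, SD, target difference or attrition rate for the 8-year follow-up. From the documents come the 90 randomised patients, the 5% level and the test. Everything else here is assumed: 45 per arm, a two-sided test, no true difference, 22% or 36% lost, and a correlation of 0.5 or 0.7 between 24-month and 8-year WORC.

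**Hand calculation.** Bias of the attender comparison = (share absent × gap) in arm A − (share absent × gap) in arm B, where the gap is how much worse, in SD, non-attenders score than attenders.
- Equal attendance and equal gaps: 0.
- 80% v 60% attending, gap 0.5 SD: 0.20 × 0.5 − 0.40 × 0.5 = −0.10 SD.
- 70% attending in both arms, gap 0.5 SD v none: 0.30 × 0.5 − 0 = 0.15 SD.

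**Simulation.** There were 10,000 replicates per scenario unless stated. Return is logistic in the WORC score, with a slope per SD in each arm. The pooled t-test on attenders was compared with the two-visit likelihood estimate. For each arm the latter is: 8-year mean of attenders + b × (24-month mean of all − 24-month mean of attenders), with b the common within-arm slope.

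| Return depends on | Scenario | t-test bias (SD) | t-test false positives | Model bias (SD) |
|---|---|---|---|---|
| 24-month score | same slope and rate | 0.00 | 4.7-5.2% | under 0.01 |
| 24-month score | slopes 1 v 0.5, or 0.5 v 0 (moderate) | 0.04-0.12 | 5.4-7.5% | under 0.01 |
| 24-month score | slope 1 in both arms, return 90% v 66% | 0.10-0.13 | 7.0-9.1% | under 0.01 |
| 24-month score | slopes 1 v 0 (near worst case) | 0.09-0.21 | 6.6-12.9% | under 0.01 |
| 8-year score | slopes 1 v 0.5, or 0.5 v 0 | 0.08-0.18 | 5.8-10.2% | 0.04-0.13 |
| 8-year score | slope 1 in both arms, return 90% v 66% (2,000 replicates) | 0.19-0.20 | 13.5-13.8% | 0.11-0.15 |
| 8-year score | slopes 1 v 0 | 0.19-0.31 | 12.8-23.9% | 0.10-0.24 |

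When return depends on the 24-month score, the model's false-positive rate is 4.3-5.4% with model-based standard errors and 4.3-6.4% with bootstrap ones. When return depends on the 8-year score, the model removes only about 20-50% of the bias, and its false-positive rate is 5.3-8.0% (moderate), 7.6-10.6% (90% v 66%) or 7.3-16.1% (1 v 0).

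Independent repeats of the normal-score scenarios, with 4,000 and 2,000 replicates, agreed within Monte Carlo error.

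**Skewed scores.** With a ceiling-skewed WORC (Beta(4,1) margins), the t-test bias is about the same. The Wilcoxon fallback does not cure it when return depends on the 24-month score: 4.6-7.2% false positives in the moderate scenarios and 6.8-11.2% in the near worst case (2,000 replicates). The skewed, Wilcoxon and bootstrap results were not repeated independently.

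**Scale.** The t-test 95% CI half-width is t(0.975) × √(2/m): 0.477 SD with m = 35 per arm and 0.526 SD with m = 29. Moderate bias with return on the 24-month score is therefore 0.043/0.477 = 9% to 0.124/0.526 = 24% of the half-width; the near worst case reaches 0.211/0.526 = 40%. The model's half-width differs from the t-test's by −8% to +2%.

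**Delta shift.** Moving one arm's non-participants by 0.5 SD moves the estimate by share lost × shift: 0.22 × 0.5 = 0.11 SD, or 0.36 × 0.5 = 0.18 SD. In the main runs with return on the 8-year score, shifts of 0.24-0.79 SD in the affected arm or arms removed what bias the model left.

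**Limit.** Every simulated patient has a 24-month score, which flatters the model.

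**The case against.** The documents show no attrition and give some reason to expect similar attendance in the two arms. Patients and assessor are to be blinded (section 4.4). No WORC, ASES, Constant or strength difference was found in the original trial. Section 4, on why the trial is needed, expects later changes in healing status to be alike in the two groups. The main contrary sign is the higher healing rate after double-row repair (section 1). A t-test on observed scores is conventional for a single-visit follow-up, and the larger simulated biases need strongly arm-dependent return, which blinding makes harder to motivate. The alternative assumes missing at random, needs data whose availability is not stated, and does little for patients with no earlier score.

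Most of this stands, and it rules out the reading that the planned test is wrong or its result biased. It does not remove the case for the model. In the normal-score runs the model was about as biased as the t-test or less, and its interval was of similar width.

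A reader might also infer that the model would cure selective return. It does not if return depends on the 8-year score itself, which is why the delta-shift analysis has to stand beside it. Nor should a large gain in precision be expected. Such gains arise from adjusting for an earlier score as a covariate, whereas here the earlier scores are post-randomisation and enter as outcomes.

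**Conclusion.** The point holds as a cheap improvement, not as an error in the plan. The text is clear: the primary comparison ignores WORC scores that the original trial collected, and the plan has no other means of handling non-participation. The consequence is uncertain. Bias is zero under equal mechanisms, about 0.04-0.12 SD with 5-8% false positives in assumed moderate scenarios where return depends on the 24-month score, and larger where it depends on the 8-year score. Attrition, arm sizes, correlation and return slopes are all assumptions, and the direction of any bias is unknown.

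The absence of a stated analysis set and participation table is missing detail and would not carry the point alone. A reader might infer that excluding patients who withdrew from the original trial breaks the randomised comparison. The documents do not support that: they give no count by arm, the effect is nil if nobody withdrew or withdrawals were balanced and alike in outcome, and withdrawn may mean that further contact was refused. That is a wording query only.

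**What to change.** Before the 8-year data are analysed, amend section 4.10 as follows.

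1. Estimate the 8-year difference, with 95% CI, from a likelihood-based repeated-measures model with arm, visit, arm-by-visit and unstructured covariance. The outcomes are the available post-randomisation WORC scores, at least 24 months, and the 8-year score. Include all randomised patients whose data may be used, by randomised arm. Use robust or bootstrap standard errors if WORC is not normal. Keep the planned t-test or Wilcoxon test as a sensitivity analysis.
2. Add a delta-shift analysis: worsen non-participants' predicted 8-year WORC by 0 to 1 SD in 0.25 SD steps, separately by arm, and report where the conclusion changes.
3. Report by arm the numbers randomised, invited, deceased, untraced, refused and assessed, and compare earlier WORC of participants and non-participants.
4. Clarify in section 4.5 whether withdrawn from the original trial means refusal of further contact.

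The cost is one paragraph of analysis text, one table and one clarification. The study coordinator already monitors visits, so the table adds little work. The downsides are the missing-at-random assumption, slightly liberal bootstrap standard errors (up to 6.4%), little help for patients with no earlier score, and the need for patient-level original-trial data. If those data cannot be obtained, keep the section 4.10 test as primary and still add the delta-shift analysis and the participation table.

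### 8-year healing rates are to be compared with no covariate, although initial tear size was recorded and linked to healing in these same patients

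*Combined protocol and SAP*

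**What the plan says.** The analysis plan is section 4.10. For the primary outcome, 8-year WORC, it states: "This analysis is a two sample independent t-test to assess whether there is a statistically significant difference between groups for the mean WORC scores". The fallback is also unadjusted: "If the sample distribution is determined to depart from normal, then a Wilcoxon rank sum test will be performed". For the secondary outcomes the plan is one sentence: "The ASES, Constant Score, and imaging healing rates will be analyzed for differences between the two groups at 8 years". It sets a 5% level for each and waives multiplicity adjustment because "treatment effectiveness is based only on the primary variable". No test, model, effect measure or covariate is named for healing, and no section names a covariate for any 8-year analysis.

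Section 1 reports from the original trial of the same patients: "However, a smaller initial tear size and double-row repair were associated with a greater healing rate". It also reports: "No significant differences between the single-row and double-row groups were found in the WORC, ASES, or Constant scores or strength at any time point".

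The size of the cohort is fixed. In the original trial "ninety patients undergoing arthroscopic rotator cuff repair were randomized to receive either a single-row or a double-row repair", and the only inclusion criterion in section 4.5 is "Randomized in the double versus single row original RCT study". Patients who withdrew from that trial are excluded.

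**The concern.** Healing is the first secondary research question, and section 4.8 treats determining the relative healing rates as essential. It is also the outcome on which the original trial reported an association with double-row repair, so the 8-year healing result will be read closely.

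Tear size is the one baseline factor that the documents tie to healing in these patients. The section on why the trial is needed now expects late changes in healing to come from tendon pathology that is alike in the two groups, but no planned step allows for a tear-size difference among those who return. In a raw comparison any such difference passes straight into the treatment difference. With at most 90 patients, precision cannot be bought by recruiting more. And because the plan is silent, whether and how to use tear size could be decided after the 8-year images have been read.

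**Working it through.** The plan gives no sample-size, power or standard-error figure, so there is nothing of its own to reproduce. What follows is illustrative.

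**Inputs for healing**
- Re-tear rates from the retrospective comparison cited in section 2 (80 shoulders, mean follow-up 35 months): small tears 13% single-row and 0% double-row; large and massive tears 44% and 29%. This is a different cohort, and section 2 quotes only these two size classes.
- Assumed: share of large tears p = 0.5; 1:1 allocation; 45 per arm (all 90 return) or 36 per arm (80% return).

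**Raw difference.** Single-row rate = 0.13 + 0.31p; double-row rate = 0.29p. At p = 0.5 in both arms: 28.5% − 14.5% = 14.0 points.

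**Standard error of the raw difference**
- Formula: √[(0.285×0.715 + 0.145×0.855)/n] = √(0.32775/n).
- n = 45: 8.53 points. n = 36: 9.54 points.

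**Standard error after standardising to a 50/50 tear mix**
- Formula: √[0.5×(0.13×0.87 + 0.44×0.56 + 0×1 + 0.29×0.71)/n] = √(0.2827/n).
- n = 45: 7.93 points. n = 36: 8.86 points.
- Reduction: 1 − 7.93/8.53 = 7.1%, and about the same at 36 per arm.
- The variance ratio is 0.32775/0.2827 = 1.16, so 90 patients give the information of roughly 104.

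With the tear mix left random (simulation), the figures hardly change:

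| Share of large tears | SE raw → standardised, 45 per arm | 36 per arm |
|---|---|---|
| 25% | 7.18 → 6.71 | 8.02 → 7.52 |
| 50% | 8.54 → 7.97 | 9.54 → 8.91 |
| 75% | 9.46 → 9.08 | 10.55 → 10.15 |

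That is a cut of about 6%, 7% and 4% respectively.

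**Chance imbalance (p = 0.5)**
- Large tears 40% in single-row and 60% in double-row: 25.4% − 17.4% = 8.0 points. Reversed: 31.6% − 11.6% = 20.0 points. The shift is 6 points either way, less than one standard error.
- An imbalance of 20 points or more has exact binomial probability 7.3% (45 per arm) or 7.6% (36 per arm).
- Median absolute shift: 2.0 points (45) or 2.5 points (36). The 90th percentile is 5.3 or 5.9 points.

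**Empty cells.** The illustration has a zero re-tear rate in one cell. In 4,000 simulated trials, ordinary main-effects logistic regression gave extreme coefficients, suggesting separation, in about 5% (45 per arm) and 9% (36 per arm). The adjusted method must allow for this. The size-specific risk differences are close (13 − 0 = 13 points and 44 − 29 = 15 points), so a pooled risk difference is a reasonable summary on these inputs.

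**WORC**
- Assumed: true difference 0.5 SD, two-sided 5%, 1:1. R is the correlation of the covariate(s) with 8-year WORC, which the documents do not give.
- Power is from the noncentral t with N − 2 − k degrees of freedom. The variance of the adjusted difference, in SD² units, is (1 − R²)(2/n)(1 + k/(N − k − 3)), with N = 2n and k covariates.

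| | 45 per arm | 36 per arm |
|---|---|---|
| Unadjusted | 65.0% | 55.3% |
| One covariate, R = 0 | 64.5% | 54.6% |
| One covariate, R = 0.2 | 66.3% | 56.3% |
| One covariate, R = 0.3 | 68.6% | 58.6% |
| One covariate, R = 0.5 | 76.8% | 66.9% |
| Two covariates, R = 0 | 64.0% | 54.0% |
| Two covariates, R = 0.5 | 76.3% | 66.3% |

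One covariate breaks even at R of about 0.11 (45 per arm) or 0.12 (36 per arm).

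**The case against.** The strongest reply is that nothing planned is wrong. An unadjusted comparison of randomised groups is valid, the plan rests its conclusion on WORC alone, and healing therefore cannot decide effectiveness. The contrast, time point and level for healing are fixed. The gain is small: on the illustrative inputs, power for the 14-point difference rises only from about 37% to 42% (45 per arm) or 31% to 35% (36 per arm). The rates behind it come from another, retrospective cohort with shorter follow-up. All of this stands and sets the size of the point. It does not remove it: a covariate already recorded, and already associated with the outcome in these patients, can be used at almost no cost.

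A reader might infer three stronger things, none of which the documents support.
- **That the primary t-test is at fault.** It is valid. No section links tear size to WORC. Section 4.8 says only that cuff integrity goes with function and strength, and in the original trial the healing association with double-row repair came with no significant difference in the scores.
- **That adjustment would materially raise power for WORC.** Tear size alone is likely to give little. A preoperative score might give more, but no section states that preoperative scores are held, and the correlation is unknown.
- **That adjustment would deal with loss to follow-up.** It handles the measured covariate only; bias from selective return at 8 years would remain.

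**Conclusion.** The point holds for healing, as a missed improvement and not an error. Initial tear size should enter the 8-year healing comparison. The expected benefit is a standard error about 7% lower (about 4% to 6% if three quarters or one quarter of tears are large) and protection from a chance shift that is typically 2 to 2.5 points and seldom as much as 6. These sizes rest on borrowed re-tear rates, an assumed tear mix and equal arms; the trial's own association between tear size and healing is reported without a magnitude. That tear size was recorded is inferred from that reported association.

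For WORC, ASES and Constant the planned or implied unadjusted comparison is acceptable. Adjustment for the preoperative score is worth adding if that score exists. For WORC, on the assumptions above, it would cost under 1 point of power if the score were not prognostic, and gain about 12 points if R were 0.5.

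**What to change.** Settle the following before any 8-year data are examined.

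1. **Healing.** Analyse by randomised group, adjusted for initial tear size in the original trial's own categories. Report the tear-size-standardised risk difference with 95% CI beside the raw rates in each group. Name one method that tolerates empty cells, for example a Mantel-Haenszel risk difference, or penalised logistic regression followed by standardisation.
2. **WORC, ASES and Constant.** Keep the t-test with Wilcoxon fallback for WORC, and name the same for ASES and Constant. If the original dataset holds each score's preoperative value, add an ANCOVA on randomised group and that value, and report the adjusted difference with 95% CI.
3. **Covariates to leave out.** Do not adjust for 24-month scores, which are post-treatment.
4. **Limits.** State that the adjustment does not address selective return at 8 years.

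The cost is a few lines in section 4.10, linkage to the original dataset, and a check on whether preoperative scores are held. No extra patients, visits or imaging are needed.

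### The planned tests for a multicentred trial leave out centre: a modest, assumption-dependent loss of precision, not a demonstrated bias

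*Combined protocol and SAP*

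**What the plan says.** Section 4.1 gives the design as "Long term follow-up of a multicentred, randomized trial". Section 1 fixes the cohort: "ninety patients undergoing arthroscopic rotator cuff repair were randomized to receive either a single-row or a double-row repair".

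For 8-year WORC, section 4.10 (Primary) states: "This analysis is a two sample independent t-test to assess whether there is a statistically significant difference between groups". It adds "The 5% significance level is employed" and a fallback: "If the sample distribution is determined to depart from normal, then a Wilcoxon rank sum test will be performed". Section 4.10 (Secondary) says only: "The ASES, Constant Score, and imaging healing rates will be analyzed for differences between the two groups at 8 years".

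No centre, surgeon or stratification term appears in any of these, and no other section supplies one. The documents do not state the number of centres or surgeons, the patients per centre, the parent trial's randomisation strata, or expected retention by arm or centre.

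**The concern.** In a multicentre trial, outcome levels may differ between centres through case mix, rehabilitation or surgical habit. A pooled two-sample test treats that variation as noise. Two things could follow.

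- **Precision and calibration.** If the arms are balanced within centre, the true sampling variance of the difference excludes centre variation, but the pooled standard error includes it. The interval is then too wide and the test rejects less often than its nominal level. The cohort is closed at ninety, so new recruits cannot restore the lost precision.
- **Bias.** The analysed set is whoever returns at 8 years and meets section 4.5, which excludes patients withdrawn from the parent trial and those who do not consent. If the centre mix of those patients differed between arms, and centres differed in WORC, the raw difference would carry part of the centre effect.

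Section 1 reports no significant WORC difference at any time point in the parent trial. Another inconclusive result is therefore possible, and an interval wider than it need be would weaken it.

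**Working it through.** The plan gives no power, effect size or standard deviation, so it has no figure to reproduce. What follows is a sensitivity calculation.

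**Inputs.** From the documents: 90 randomised, 5% level. Assumed: two-sided test, 45 per arm, and a share ρ of WORC variance due to centre of 1%, 5%, 10% or 15%. Three centres are assumed for the degrees of freedom, and two equal centres for the bias example.

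**1. Precision.** The ratio of adjusted to unadjusted standard error is √(1 − ρ). With three centres, residual degrees of freedom go from 90 − 2 = 88 to 90 − 4 = 86. A rough cost is √(88/86) = 1.012, about 1%. The difference detectable at 80% power without centre is (1.960 + 0.842) × √(2/45) = 0.591 SD. With centre in the model it is 0.591 × √(1 − ρ), before the degrees-of-freedom cost.

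**2. Calibration.** If the arms are balanced within centre, the pooled statistic has variance of about 1 − ρ. Its true type I error is then 2 × [1 − Φ(1.960/√(1 − ρ))].

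| ρ | SE ratio | SE ratio net of df cost | Detectable difference (SD) | True type I error of pooled test |
|---|---|---|---|---|
| 1% | 0.995 | 1.006 | 0.588 | 4.9% |
| 5% | 0.975 | 0.986 | 0.576 | 4.4% |
| 10% | 0.949 | 0.960 | 0.560 | 3.9% |
| 15% | 0.922 | 0.933 | 0.545 | 3.4% |

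In patients, 90/(1 − ρ) runs from 90.9 to 105.9, so adjustment is worth about 1 to 16 extra patients before the degrees-of-freedom cost. If only 60% returned (27 per arm), the detectable difference would be 0.762 SD unadjusted and 0.759 to 0.703 SD adjusted.

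**3. What bias would require.** With two equal centres, a centre variance share of ρ means the centres differ by 2√ρ SD. If the arms differ by s in the proportion of patients from one centre, the bias is s × 2√ρ.

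- s = 0.10: 0.02 SD (ρ = 1%) to 0.08 SD (ρ = 15%).
- s = 0.30: 0.06 SD to 0.23 SD.

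In simulation (20,000 runs per setting, 27 to 45 per arm, ρ of 5% to 10%), s fixed at 0.20 gave the plain t-test a type I error of about 5.5% to 7.8%. At s = 0.30 it was about 7.4% to 12.5%. With centre in the model it was about 5% throughout.

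Reaching s = 0.20 through loss alone takes a strong pattern. Starting from two equal centres balanced at randomisation, one arm could retain 90% and 60% and the other 60% and 90%. The shares from the first centre are then 0.90/1.50 = 0.60 and 0.60/1.50 = 0.40.

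**The case against.** The strongest reply is that the planned test is not invalid. Under simple randomisation, chance imbalance between centres is already part of the t-test's standard error. Under balance within centre, the test errs on the safe side. Both statements are right, and they limit the point to precision and calibration.

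The size is also wholly assumed. At a 1% variance share the gain is smaller than the degrees-of-freedom cost, and many small centres would raise that cost. This stands, and it is why the low end belongs in the range.

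A reader might look for proof of centre differences in three places. None of them supports it.

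- Section 4.2 leaves stitch type open ("Either simple or mattress sutures were used at the discretion of the surgeon"), and section 2 cites an animal study in which stitch and anchor configuration changed pull-out strength about two-fold. That study concerns initial fixation, not patient-reported quality of life at 8 years. Section 2 itself says that reliance on initial fixation falls as healing proceeds.
- Section 4.7 refers to evaluators in the plural. But section 4.9 has the patient complete the WORC, and the assessor's examination feeds the Constant score, so assessor differences do not bear on the primary endpoint. Section 4.4 also says that examination and questionnaire administration are standardised.
- Surgeon discretion operates at surgeon level, and the documents do not say how surgeons map to centres.

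What survives the reply is the omission itself. The plan calls the trial multicentred and never uses that structure.

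**Conclusion.** The point holds as a modest matter of precision and calibration. Centre is missing from the primary test, its fallback and every secondary comparison. With 45 per arm and a centre share of 1% to 15%, adjustment lowers the standard error by about 0.5% to 8% before a cost of about 1% for three centres. The net effect runs from about zero to about 7%. If the arms are balanced within centre, the pooled test's true level is about 4.9% to 3.4% instead of 5%. All of this rests on the assumed variance share, the even split, the number of centres and full retention.

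A reader might infer that 8 years of loss has already confounded the arms by centre. The documents do not support that. They give no retention figures. Loss that varies by centre but is similar in both arms leaves the arms balanced. Bias needs a difference in centre mix between the analysed arms together with real centre differences in WORC, and neither is shown. Section 4.4 says patients and assessor are blinded, so there is no evident reason for return to depend on arm in opposite ways at different centres. The bias figures above show what such a pattern would do; they do not forecast it.

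**What to change.** Amend section 4.10 before unblinding:

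- **Primary.** Estimate the 8-year WORC difference, with its 95% interval, from a linear model with arm and randomising centre as fixed factors. If the parent trial stratified its randomisation, use those strata.
- **Small centres.** State a numeric pooling rule. One proposal is a tenth of the assumed arm size, 45 × 0.10 = 4.5: pool any centre with fewer than 5 analysed patients in either arm into one stratum. The sponsor should confirm the threshold once centre sizes are known and before outcomes are seen by arm.
- **Fallback.** Replace the Wilcoxon rank sum test with its centre-stratified form (van Elteren), using the same strata.
- **Secondary.** Use the same centre factor for ASES and Constant, and a Mantel-Haenszel comparison stratified by centre for healing.
- **Reporting.** Tabulate retention by arm and centre, so that readers can see whether centre mix differs between the analysed arms.
- **Sensitivity.** Keep the plain t-test.

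The cost is plan wording, a variable that should already be on record for every randomised patient, a few degrees of freedom and the pooling rule. If centre explains almost none of the variance, the change gains nothing and loses about 1% in precision. It does not deal with loss related to outcome within a centre, which needs its own missing-data plan.
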